Aim 1: We calculated statistical power for the target sample size of 675, with approximately 337 participants enrolled into both TEAM and TECH. After adjusting for the multiple testing in Aim 1 (2 tests) and considering 25% attrition, a sample size of 505 (approximately 252 per treatment group) will provide over 99.9% power for the hypothesis test for Aim 1. Among patients enrolled in the specialty medical home at that time who met active behavioral criteria (PHQ-4 >= 6), there was a significantly greater change in TECH (n=73; ES .49) versus TEAM (n=106; ES .36) for the behavioral composite but both approaches were associated with significant change over time (p=.005). Both approaches were also associated with significant improvement in the biological composite for both TEAM (ES .22) and TECH (ES .16). With the IBD SMH models of care being clinically operational at all three sites, we are collecting ongoing useful and robust information that has been published. In our most recent analyses of our clinical research registry tracking our TEAM approach (n=280), our most recent analyses show effect sizes comparable to these initial findings for both approaches.

Aim 2: We considered both subgroup analyses and formal tests of moderation. Subgroup analyses – Based on current data, our subgroups are relatively evenly proportioned. We expect that the smallest subgroup will be 42% of the sample and the largest will be 58% of the sample. Thus, our expected subgroup sizes after 25% attrition are between 212 and 293 for projected enrollment. For this range of subgroup Ns, we expect 0.80 power to detect small treatment effects ranging between 0.26 and 0.30. Moderation – We used Monte Carlo methods (100 runs) to simulate the binary moderator (M) and treatment (X) (both p=0.5), assuming M independent of X as expected in a randomized trial. Considering a range of effect sizes for B1, B2, and B3, we estimated the outcome Y as Y=B1\*X+B2\*M+B3\*X\*M+ $\varepsilon$ , where  $\varepsilon$ ^N(0,1). We averaged across

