#### **Quantitative Analysis**

We will conduct descriptive analyses and multivariate modeling of data to examine changes in outcomes over time and explore moderating variables. All analyses will be intent to treat and conducted as described in our analytic plan and associated protocol. If diagnostic or sensitivity analyses dictate changes to those plans, we will clearly identify subsequent analyses as ad hoc or otherwise deviating from an a priori plan, including labeling subgroup and interaction analyses as confirmatory, exploratory, or post hoc. Our statistician will remain masked to study arm to reduce bias.

Prior to hypothesis testing for Aims 1 and 2, data will be explored by descriptive data analysis. Summary statistics including means, standard deviations, medians, and ranges for continuous variables, or frequencies and percentages for categorical variables, will be presented for the entire sample and stratified by approach at each time point. We will assess the balance of key covariates by visually assessing the standardized differences. We will conduct baseline data analysis for each outcome to explore any pre-intervention differences in outcomes between TEAM and TECH at baseline. Two-sided Wald T-test or Wald F-test using the generalized linear mixed models (GLMMs) with normally distributed random effects for three sites will be used. This estimating method using GLMMs will produce consistent estimations of the regression parameters under the missing at random (MAR) or missing completely at random (MCAR) mechanism. The MAR assumption will be verified in the sensitivity analysis (see handling missing data in quantitative analyses). Distributions of outcomes and key covariates over time will also be visually examined to identify systematic departures from normality and overall pattern over time, assisting us in evaluating the distribution of data and determining if assumptions are met for subsequent modeling approaches. We will conduct statistical analysis on transformed outcomes using Box Cox- or log-transformation to address any asymmetry.

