Aim 1 will examine the impact of TEAM vs. TECH on the primary and secondary outcomes and will determine if changes in outcomes over time are different between the two groups. We will fit the GLMMs to associate each outcome with the intervention (TEAM vs. TECH) and other covariates of interest. To account for the within-patient correlation in longitudinal data and to reflect potential differences among three sites, we will add normally distributed random effects for patients and sites in addition to the fixed effects for intervention and covariates of interest. An inference of the intervention effects for each outcome will be carried out using Wald test based on the either F-distribution or Chi-square distribution as appropriate. For each outcome, the null hypothesis of homogeneous change in outcomes overtime between TEAM and TECH will be examined by testing the treatment-by-time interaction effect on each outcome. In the absence of significant interaction effects, the marginal difference in outcomes between TEAM and TECH will be examined using the same GLMMs without the interaction effect. All hypothesis tests for Aim 1 will be conducted at the overall significance level of 0.05. The score changes from baseline to each time point and their difference between TEAM and TECH will be estimated with 95% confidence intervals.

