Given our study Aim 2 to understand how TEAM and TECH provide different benefits to individuals with different characteristics, we will explore potential heterogeneity of treatment effects in clinical response between subgroups of patients defined using patients' baseline characteristics. All co-variates will be identified a-priori. For Aim 2.a, we will examine whether and how the effect of TEAM and TECH approaches on BH symptom severity varies between patients with a high level of IBD disease activity (HBI or UCAI score > 4) and patients with low disease activity (HBI or UCAI score <=4) at baseline. IBD disease activity and effect of TEAM and TECH approach will also be assessed using a recently developed, validated, and preferred measure of disease activity for Crohn's disease and UC (PRO-2). 63,64 For statistical inference, we will fit the same GLMMs as described in Aim 1 and will include the higher order interaction terms with subgroups of patients defined by IBD activity. The null hypothesis of homogenous treatment effect between patients with high and low IBD activity in each outcome will be examined via interaction analysis (three-way interaction of time, treatment, and subgroup of IBD severity; two-way interaction of treatment and subgroup of IBD severity in the absence of a significant three-way interaction effect) using Wald test based on either F-distribution or Chisquare distribution as appropriate at the significance level of 0.05. In the presence of statistically significant treatment heterogeneity, the score change in BH symptom severity from baseline to each time point and their difference between TEAM and TECH will be estimated with 95% confidence intervals for subgroup of patients defined by IBD severity. For Aim 2.b, we will explore whether and how the effect of TEAM and TECH approaches on primary outcomes varies between young (age<=30) and older (age>30) patients. We will also examine the impact of TEAM and TECH on patients with differing IBD diagnoses, namely ulcerative colitis and Crohn's disease. Further, we will explore the effect of site differences, behavioral health history, insurance type (public vs. not), e-health literacy, and medications on response to TEAM or TECH intervention as secondary and exploratory analyses. For statistical inference, the same hypothesis test and statistical model described in Aim 2.a will be used. We will make a Bonferroni correction for multiple testing in order to conduct subgroup analyses at the overall significance level of 0.05. In the presence of statistically significant treatment heterogeneity,

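### Aim 1 allows up to four tests on the two primary outcomes but adjusts for two, and states neither a level per test nor which step decides

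*Combined protocol and SAP*

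**What the plan says.** Aim 1 has two primary outcomes, IBD symptom severity and behavioral health symptom severity (Aims; Measures). Under Quantitative Analysis, the null hypothesis for each outcome is that change over time is the same in both arms, and it is tested by the treatment-by-time interaction. A second step follows: "In the absence of significant interaction effects, the marginal difference in outcomes between TEAM and TECH will be examined using the same GLMMs", now without the interaction term. The level is set in one sentence: "All hypothesis tests for Aim 1 will be conducted at the overall significance level of 0.05". The scope of Aim 1 is wider than the primary outcomes: "Aim 1 will examine the impact of TEAM vs. TECH on the primary and secondary outcomes".

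The only count of tests is in Sample Size and Power Calculations: "After adjusting for the multiple testing in Aim 1 (2 tests) and considering 25% attrition". That section then claims "over 99.9% power for the hypothesis test for Aim 1", in the singular. It gives neither the adjustment method nor the resulting level.

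Aim 2 is more explicit. Its fallback is the "two-way interaction of treatment and subgroup of IBD severity in the absence of a significant three-way interaction effect", run as a Wald test at 0.05, and a method is named for the subgroup analyses: "We will make a Bonferroni correction for multiple testing in order to conduct subgroup analyses at the overall significance level of 0.05".

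**The concern.** A two-step rule gives each outcome two chances to reach significance. With two primary outcomes there are up to four, and the plan's count covers two. The promise of an overall 0.05 can be kept in several ways, but each needs a statement that the plan does not make: a smaller level per test, or a rule that only one step is confirmatory.

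The primary conclusion is at stake. If both steps count at 0.025, a false claim of a TEAM-TECH difference is more likely than stated. If only treatment-by-time counts, a significant marginal difference could not be claimed as confirmatory. If the rule is chosen after the results are seen, either claim is open to challenge.

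**Working it through.** **Inputs from the documents.** Overall level 0.05 and two steps per outcome (Quantitative Analysis); two primary outcomes (Aims); two tests counted and about 252 per arm after 25% attrition (Sample Size and Power Calculations); self-report at baseline, 6 and 12 months (Compensation for Participation).

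**Assumptions.** Level per test a = 0.025; a positive result at either step counts; compound symmetry with baseline as one of three outcome values. Under compound symmetry the treatment-by-time test (2 df) and the marginal test are independent. The correlation between the two outcomes is not given, so it is varied.

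**Reproducing the stated level.** Two tests at 0.025: 2 x 0.025 = 0.05 as a bound, and 1 - (1 - 0.025)^2 = 0.0494 if independent. So 0.05 is consistent with exactly two tests at 0.025.

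**Both steps counting.**
- Per outcome: 1 - (1 - 0.025)^2 = 0.0494.
- Two independent outcomes: 1 - (1 - 0.025)^4 = 0.0963. Upper bound: 4 x 0.025 = 0.10.
- Correlated outcomes, by simulation:

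| Outcome correlation | Both steps, 0.025 each | Both steps, 0.0125 each | Treatment-by-time only, 0.025 |
|---|---|---|---|
| 0 | 0.096 | 0.049 | 0.049 |
| 0.5 | 0.091 | 0.047 | 0.046 |
| 0.7 | 0.085 | 0.044 | 0.044 |
| 0.9 | 0.071 | 0.037 | 0.037 |

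Against 0.05, the second column is a ratio of 0.071/0.05 = 1.4 to 0.096/0.05 = 1.9. It returns to about 0.049 only if the two outcomes are perfectly correlated.

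**If the two tests are the two steps instead.** At 0.025 per step the error is 0.0494 for one outcome. Across both outcomes it is again up to 0.0963. The count is equally short.

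**Power per outcome of the alternatives.** The plan gives no between-arm target, so a sustained 0.25 SD difference at 6 and 12 months is used for illustration: d = (0, 0.25, 0.25), mean 0.1667, n = 252 per arm, within-patient correlation r.
- Treatment-by-time non-centrality: (n/2) x sum of (d - mean)^2 / (1 - r) = 126 x 0.04167 / (1 - r) = 10.5 at r = 0.5 and 17.5 at r = 0.7. Power at 0.025 on 2 df: 0.757 / 0.947.
- Marginal test: z = 0.1667 / sqrt[(2/n)(1 + 2r)/3] = 2.29 / 2.09. Power at 0.025: 0.520 / 0.440.
- Both steps at 0.025: 1 - (0.243)(0.480) = 0.883, and 1 - (0.053)(0.560) = 0.970.
- Both steps at 0.0125, by the same formulas: 0.809 / 0.943.

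**The case against.** The strongest reply is that the overall-level sentence, read literally, covers both steps and promises control. No document states 0.025 per test, and none says that either step is enough. A reader might infer that the plan's error rate is 0.07 to 0.096, or even 0.185 from four unadjusted independent tests at 0.05 (1 - 0.95^4). The documents do not support either as the plan's rate. Both figures follow only from rules that the plan does not state.

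The text also leans towards treatment-by-time as the Aim 1 test. The section opens by asking whether change over time differs between arms, attaches its null hypothesis only to the interaction, and reports between-arm differences in change from baseline. The power section speaks of one hypothesis test. On that reading there are exactly two tests and 0.05 holds.

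This reply narrows the point without removing it. No passage calls the marginal step descriptive. The level sentence comes directly after that step and refers to all Aim 1 tests. The parallel fallback in Aim 2 is a formal test.

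It is also fair to say that the secondary outcomes are labelled secondary and that a count of two leaves no room for them. Still, Aim 1 includes them, and the plan does not place them outside the 0.05. Finally, an error of 0.07 needs an outcome correlation near 0.9, the visit times come from a payment schedule, and 0.25 SD is illustrative.

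**Conclusion.** The point holds as a missing decision rule, together with a count of tests that falls short of the procedure described. Four tests are possible and two are counted, whichever pair the count refers to. The size is conditional. With 0.025 per test and either step sufficient, the overall error is about 0.09 for outcome correlations of 0 to 0.5, with a range of 0.07 (correlation 0.9) to 0.096 (correlation 0) and a ceiling of 0.10. With treatment-by-time as the sole confirmatory test, the 0.05 is kept; the plan leans towards this but does not state it. The plan should be amended, because a reader cannot tell which rule applies. Confidence is medium: the gap is plain in the text, but the inflation rests on two unstated assumptions and an unknown correlation.

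**What to change.** Before unmasking, add a few sentences to the Aim 1 paragraph:

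1. The confirmatory family is the two primary outcomes; secondary outcomes lie outside it.
2. Preferably, treatment-by-time is the sole confirmatory test for each outcome, at 0.025 (or Holm across the two outcomes). Baseline stays as an outcome value, as the planned change-from-baseline estimates imply. The marginal difference is labelled descriptive.
3. Alternatively, if both steps are to count, each is tested at 0.0125.

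No new data are needed. The change can still be made without knowledge of results by arm, since the plan says: "Our statistician will remain masked to study arm to reduce bias".

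The cost is power. For the illustrative sustained 0.25 SD effect at within-patient correlation 0.5 / 0.7, power per outcome moves from 88% / 97% (both steps at 0.025) to 76% / 95% with treatment-by-time only at 0.025, or to 81% / 94% with both steps at 0.0125. The preferred option also gives up the second chance: a positive marginal result alone would support no confirmatory claim. It is preferred because it matches the null hypothesis that the plan already states; the alternative is also valid.

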
estimation of score changes in each outcome and their difference between TEAM and TECH will be presented with 95% confidence intervals for each subgroup of patients.

In handling missing data in quantitative analyses, we will attempt to determine the reasons for missing data and dropouts. The MAR assumption will be examined by comparing baseline characteristics between participants with and without missing data and conducting sensitivity analysis by repeating the main analyses without participants with missing data. If we observe statistical evidence that data are not MAR, we will stratify the participants into subgroups that share the same missing data pattern and estimate the statistical model separately for each missing data pattern. The results of all missing data analyses will be presented, and the sensitivity of our inference to the assumptions and approaches will be included in the interpretation of results.

COVID Considerations for Aims 1-2: Of our 675 projected participants, 32 were enrolled and completed their 6-month/primary outcomes surveys before the beginning of the COVID-19 (i.e., prior to March 12, 2020); 211 are potentially COVID-confounded (i.e., enrolled prior to or during the acute phase of the pandemic and were followed during it), and 432 were enrolled in the post-COVID phase of the study (after June 2021). Primary analyses will focus on the full sample of N=675, controlling for whether the participant was COVID-confounded. In sensitivity analyses, we will include only participants enrolled during the post-COVID phase. Effect sizes from sensitivity analyses will be assessed to evaluate whether findings are similar to those from the primary analyses.

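### If baseline is a response in the Aim 1 mixed model, as the text implies, the fallback marginal difference averages in the pre-treatment visit and understates a constant TEAM-TECH effect

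*Combined protocol and SAP*

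**What the plan says.** All references are to the Combined protocol and SAP.

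- **Quantitative Analysis, Aim 1.** Each outcome is modelled with a GLMM that has random patient and site effects. The null of equal change over time is tested through treatment-by-time. If that is not significant, "the marginal difference in outcomes between TEAM and TECH will be examined using the same GLMMs without the interaction effect". The paragraph ends: "The score changes from baseline to each time point and their difference between TEAM and TECH will be estimated with 95% confidence intervals". On error control it says "All hypothesis tests for Aim 1 will be conducted at the overall significance level of 0.05".
- **Quantitative Analysis, Aim 2.** The same pattern is used for moderation: a three-way term first, then the "two-way interaction of treatment and subgroup of IBD severity in the absence of a significant three-way interaction effect".
- **Compensation for Participation.** Self-report is paid at baseline, 6 months and 12 months. The numbering skips Timepoint 2 for self-report.
- **COVID Considerations for Aims 1-2.** The only indication of a primary time point is in an enrolment count of those who "completed their 6-month/primary outcomes surveys before the beginning of the COVID-19".

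No section says whether the baseline score is a response or a covariate. The Covariates section lists no baseline outcome score, and nothing limits the marginal difference to post-baseline visits.

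**The concern.** A model that tests equality of change over time and yields changes from baseline most naturally has baseline as one of its repeated responses. In such a model the treatment effect is the treatment-by-time term, because the arms have the same expected mean before treatment starts. Dropping that term forces a single arm difference on all visits, including the one where the expected difference is zero. The result is neither the 6-month effect nor the average effect after treatment.

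The step applies when the interaction is not significant, which is likely if the true difference is small. The result read from it could therefore be a diluted difference with a confidence interval centred on the wrong quantity. The Aim 2 fallback dilutes a treatment-by-subgroup difference in the same way.

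**Working it through.** **Inputs from the plan.** The sample size is 675. The power statement reads "After adjusting for the multiple testing in Aim 1 (2 tests) and considering 25% attrition". 675 × 0.75 = 506, against 505 stated, or about 252 per arm. Self-report visits are at 0, 6 and 12 months.

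**Assumptions.** Unit SD; random patient intercept, so equal within-patient correlation ρ (not given; 0.3 to 0.7 examined, 0.5 for illustration); categorical time; two-sided tests at 0.05, normal approximation. The plan states two-sided testing only for the baseline comparison. The illustrative d = 0.13 is the pilot difference 0.49 − 0.36, if both are on one SD scale.

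**The plan's own figure.** The plan gives over 99.9% power for Aim 1 without an effect size. At 252 per arm and two-sided 0.025, a between-arm difference of 0.49 gives 0.9994, a within-arm change of 0.36 gives 0.9997, and a between-arm difference of 0.13 gives 0.217. So the figure does not correspond to the pilot between-arm difference, and the plan gives no figure for the fallback.

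**Step 1: what the fallback estimates.** With complete data every visit has equal weight. For a constant effect d after baseline: (0 + d + d)/3 = 0.67d.

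**Step 2: attrition.** Suppose 25% of patients have baseline only. Completers contribute weight 0.75/(1+2ρ) to each visit, and the others add 0.25 to baseline. The weight on the two post-baseline visits is 1.5/(2.5 + 0.5ρ):
- ρ = 0.3: 1.5/2.65 = 0.566
- ρ = 0.5: 1.5/2.75 = 0.545
- ρ = 0.7: 1.5/2.85 = 0.526

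The loss is 43% to 47%. If half of the dropouts miss only month 12, it is 40% to 42%.

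**Step 3: effect shape (complete data, relative to the 6-month effect).**
- 12-month effect half as large: (0 + 1 + 0.5)/3 = 0.50
- 1.5 times as large: (0 + 1 + 1.5)/3 = 0.83
- twice as large: (0 + 1 + 2)/3 = 1.00, no loss

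**Step 4: power at d = 0.13, ρ = 0.5, 252 per arm, complete data.** SE = √(2v/252), where v is the per-arm variance.
- Fallback: v = (1 + 2ρ)/3 = 0.667; SE 0.0727; estimate 0.0867; z = 1.19; power 22%.
- Baseline-adjusted mean of the two post-baseline visits: v = (1 + ρ)/2 − ρ² = 0.50; SE 0.0630; z = 2.06; power 54%.
- Baseline-adjusted 6-month contrast: v = 1 − ρ² = 0.75; SE 0.0771; z = 1.69; power 39%.

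**Step 5: how often the fallback is used, and the two steps together.** In 20,000 simulated trials at d = 0.13 the 2-df interaction test was non-significant in 69% (52% at ρ = 0.7), and the mean fallback estimate in those trials was still about 0.67d. With complete data and equal correlation the two steps are independent, so the chance that at least one rejects is 1 − 0.69 × 0.78 = 46%.

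| d | Reach fallback | Fallback power | Post-baseline mean | 6-month contrast | Either step rejects |
|---|---|---|---|---|---|
| 0.13 | 69% | 22% | 54% | 39% | 46% |
| 0.25 | 17% | 63% | 98% | 90% | 94% |

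At d = 0.25 the fallback's 95% interval covers 0.25 about 79% of the time. The last column is helped by two tests each at 0.05: with no true difference, 1 − 0.95² = 9.75% of trials reject at one step or the other.

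**The case against.** Four points stand against a stronger reading.

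1. **Baseline as a response is inferred.** Changes from baseline could also come from a change-score model, or from post-baseline outcomes adjusted for baseline. In either case the treatment term without interaction is a post-baseline average and nothing is diluted. This stands. It makes the finding conditional, but it also shows that the estimand turns on something the plan leaves unsaid.
2. **The fallback is not the only Aim 1 result.** The difference in change at each time point is promised with 95% intervals, and for Aim 1 this does not depend on the interaction test. A reader might infer that no sound 6-month estimate will be reported; the text does not support that. In Aim 2 the protection is weaker, because subgroup estimates are planned only when heterogeneity is significant.
3. **Fallback power is not the plan's power.** A reader might infer that the whole Aim 1 procedure is biased toward no difference. The last column of the table does not show that: rejection at either step is more frequent than for a single 6-month contrast, partly because of the two chances at 0.05.
4. **The loss is not a fixed fraction.** A reader might take a quarter to a third as a general range. One quarter, (0 + d + d + d)/4 = 0.75d, needs a fourth self-report visit that the documents do not describe. Attrition and effect shape move the loss in both directions.

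The sample size section also says that a null Aim 1 could still suggest that TECH is feasible and lets TEAM be used more efficiently. A reader might take this as a plan to claim equivalence from the fallback. The text does not link the two.

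**Conclusion.** The point holds conditionally. If baseline is a response, as the Aim 1 wording implies, the fallback estimates 0.67d with three visits, complete data and a constant effect. It estimates 0.53d to 0.57d if a quarter of patients have no post-baseline data, and it equals the 6-month effect only if the effect doubles by month 12. At an illustrative 0.13 SD it would be the operative test in most trials at ρ = 0.5, with less power than either baseline-adjusted contrast. The correlation and the 0.13 are assumptions, not plan values.

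The defect is confined to the fallback test and its estimate in Aim 1 and to the treatment-by-subgroup fallback in Aim 2. A related gap is that neither Aim 1 test is designated as a 6-month contrast, although 6 months is called, in passing, the primary outcomes survey.

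**What to change.** - Remove the step that drops the interaction while baseline is in the response.
- State how baseline enters: either as a response with a common baseline mean for both arms, or as a covariate with only post-baseline visits as responses.
- Prespecify one post-baseline contrast as the Aim 1 test, carried out whatever the interaction shows. Two choices are defensible: the 6-month contrast, which fits the COVID paragraph, or the average of the post-baseline visits, which has more power if the effect is constant.
- In Aim 2, test the subgroup difference in that same contrast and drop the two-way fallback.

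A single prespecified contrast also removes the two chances at 0.05 for each outcome. The cost is SAP wording and one changed model statement. No new data are needed.

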scenarios to determine the typical effect of B3 that can be detected with our current and projected sample sizes after 25% attrition. B3 can be interpreted as the difference between the treatment effect size among those with M=0 (D0=B1). With our projected sample sizes (N=505 after 25% attrition), we expect 0.80 power to detect a significant interaction when the magnitude of B3 is at least 0.50. To provide context for these effect sizes, we note that a B3 of 0.50 could correspond, for example, to a moderate effect of X in one subgroup (e.g., D1=0.60) and a small effect of X in the other subgroup (e.g., D0=0.10).

Our sample size calculations are consistent with the literature for both TEAM and TECH for behavioral and physical disease severity outcomes and there is literature supporting engagement and better outcomes with TECH approach with the younger cohort and those with higher eHealth-literacy. However, the research proposed will be beneficial even if we do not prove our hypotheses. For example, even if TEAM and TECH do not differ in Aim 1, the results can still suggest that TECH is feasible and allows TEAM to be utilized more efficiently. In Aim 2, even if we do not show a strong differential impact of the interventions based on IBD activity, we will still learn valuable information about which subgroups of behaviorally complex IBD patients have highest engagement and impact with each approach.

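### Aim 2 provides subgroup TEAM-TECH differences with 95% CIs when heterogeneity is statistically significant and makes no provision for reporting them, or the interaction estimate, otherwise

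*Combined protocol and SAP*

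**What the plan says.** All references are to the combined protocol and SAP.

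- **Quantitative Analysis, Aim 2.a (baseline IBD activity).** A three-way interaction of time, treatment and subgroup is tested first, then the "two-way interaction of treatment and subgroup of IBD severity in the absence of a significant three-way interaction effect", each "using Wald test based on either F-distribution or Chisquare distribution as appropriate at the significance level of 0.05". The estimation sentence follows: "In the presence of statistically significant treatment heterogeneity, the score change in BH symptom severity from baseline to each time point", together with the TEAM-TECH difference, will be estimated with 95% CIs by IBD-severity subgroup.
- **Quantitative Analysis, Aim 2.b (age) and the other moderators.** The same opening condition is repeated, after which "estimation of score changes in each outcome and their difference between TEAM and TECH will be presented with 95% confidence intervals" for each subgroup. Just before it comes the multiplicity rule: "We will make a Bonferroni correction for multiple testing in order to conduct subgroup analyses at the overall significance level of 0.05". The number of tests is not given.
- **Sample Size and Power Calculations, Aim 2.** With 505 patients after attrition, "we expect 0.80 power to detect a significant interaction when the magnitude of B3 is at least 0.50". The same section says that, even without a strong differential impact by IBD activity, the trial will still show which subgroups have the highest engagement and impact with each approach.
- **Quantitative Analysis, Aim 1.** Score changes and the TEAM-TECH difference are estimated with 95% CIs, with no condition on a test.

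**The concern.** Aim 2 is one of the protocol's primary aims, and its purpose is to establish which patients benefit most from each approach. That is a question about the size of the TEAM-TECH difference in each subgroup, so the estimates and their intervals are the answer. Making them depend on a significant interaction test has two consequences.

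First, when the test is not significant the reader gets a test result but no subgroup difference and no interaction estimate with a CI. A trial that rules out a large interaction cannot then be told apart from one that was merely imprecise.

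Second, estimates that appear only after passing a threshold are selected for being large. On average they overstate the heterogeneity, and their nominal 95% intervals can cover the truth less often than 95%. Anyone pooling the subgroup results with other trials would inherit that selection.

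**Working it through.** **Inputs.** From Sample Size and Power Calculations: N = 505 after 25% attrition; treatment and moderator both binary with p = 0.5; residual SD 1; 0.80 power at B3 = 0.50. From Quantitative Analysis: alpha 0.05 for the interaction test. Two-sidedness is stated for the baseline comparison ("Two-sided Wald T-test or Wald F-test using the generalized linear mixed models (GLMMs") and is assumed here for the interaction test.

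**Step 1: reproduce the plan's figure.** With two balanced binary factors, Var(B3) = 16·SD²/N, so SE = 4/√505 = 0.178. Power at 0.50 is Φ(0.50/0.178 − 1.96) = Φ(0.85) = 0.80, as stated. With a 42/58 moderator split, the most uneven the plan expects, power is 0.79.

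**Step 2: what passes.** At alpha 0.05 subgroup estimates appear only if the estimated |B3| is at least 1.96 × 0.178 = 0.349.

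**Step 3: consequences by true B3.** Write d = B3/SE and P = Φ(d − 1.96); the wrong-sign tail is negligible here.

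- Chance that no subgroup estimate is produced: 1 − P.
- Mean interaction among those reported: SE × [d + φ(1.96 − d)/P].
- Bias in one subgroup's TEAM-TECH difference: half the excess in B3. B3 is the difference of two independent subgroup effects with equal variance, so selection pushes each by half, in opposite directions.
- Coverage of the reported 95% CI for B3: [0.975 − Φ(1.96 − d)]/P for the values below.

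| True B3 | No estimate | Mean reported B3 | Ratio to truth | Bias, one subgroup (SD) | CI coverage |
|---|---|---|---|---|---|
| 0.50 (planned) | 20% | 0.562 | 1.12 | 0.03 | 97% |
| 0.30 (assumed) | 61% | 0.474 | 1.58 | 0.09 | 94% |
| 0.25 (assumed) | 71% | 0.460 | 1.84 | 0.10 | 91% |

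Example for B3 = 0.50: d = 2.81, φ(−0.85) = 0.278 and P = 0.802, so the mean is 0.178 × (2.81 + 0.278/0.802) = 0.562; the subgroup bias is (0.562 − 0.50)/2 = 0.03; coverage is (0.975 − 0.198)/0.802 = 0.97. Simulation of the selection gives the same results. For the plan's own illustration (effects of 0.60 and 0.10 in the two subgroups), the reported means are 0.63 and 0.07.

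**Step 4: Bonferroni.** The number of tests is not stated, so a range is shown. At B3 = 0.50:

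| Tests | Alpha | Power | Ratio to truth |
|---|---|---|---|
| 2 | 0.025 | 0.72 | 1.17 |
| 4 | 0.0125 | 0.62 | 1.22 |
| 8 | 0.00625 | 0.53 | 1.27 |

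With four tests and a true B3 of 0.25, power is 14%, the ratio 2.14 and coverage 82%.

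**Step 5: are smaller interactions plausible?** The prior data in the power section give whole within-arm changes in the behavioral composite of 0.49 (TECH) and 0.36 (TEAM), a gap of 0.13. A B3 of 0.50 is at least as large as either arm's entire prior change. This makes smaller values worth considering; it does not estimate B3.

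**Step 6: without the condition.** The mean reported B3 equals the true B3 and the intervals keep nominal coverage. Approximate 95% half-widths in SD units are 1.96 × 0.178 = 0.35 for the interaction, and 1.96 × 2/√n for a subgroup: 0.27 for n = 212 and 0.23 for n = 293, the plan's expected range.

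**The case against.** The plan never says that subgroup estimates will be withheld. It says they will be given when heterogeneity is significant. The power section treats subgroup analyses separately from formal tests of moderation, gives them their own power figures, and promises subgroup information even if the differential impact is weak. On that reading the defect is an ambiguity rather than a rule of suppression. Requiring a significant interaction before showing subgroup effects is also a common guard against over-reading them, and part of this work is described as exploratory.

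The ambiguity argument stands in part: the intention may be to report everything. But the only sentences that say when subgroup differences are estimated carry the condition, and the planned descriptive tables are for the whole sample and by approach, not by moderator. The guard against over-reading is already supplied by the adjusted interaction test and does not require leaving estimates out.

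Three stronger readings are tempting, and the documents do not support them.

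- **The interaction test is underpowered.** At the planned B3 and alpha 0.05 its 0.80 power reproduces. Power is low only for smaller interactions, or is reduced by the Bonferroni correction.
- **The published subgroup effects will be badly exaggerated.** At the planned B3 the interaction is inflated by 12%, a subgroup difference is off by 0.03 SD, and coverage is not below 95%. The larger multiples describe B3, not the subgroup differences to which the condition applies.
- **Aim 2 yields nothing if the test misses.** The test result remains. What is missing is any stated estimate with its interval.

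**Conclusion.** The point holds as a gap in the reporting rule with a selection effect attached. At the planned interaction the selection bias is small, but there is a one-in-five chance of having no subgroup estimate for a given moderator and outcome. If the true interaction is around 0.25 to 0.30, that chance is 61% to 71%, reported interactions average 1.6 to 1.8 times the truth, and coverage slips to 91% to 94%. Bonferroni correction moves all of these in the wrong direction.

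The wording finding is firm. The sizes rest on assumptions: the true B3 is unknown; the number of Bonferroni tests is not stated, and alpha 0.05 may be what applies to the Aim 2.a sentence; and the calculation uses one cross-sectional contrast, as the plan's power model does, rather than the repeated-measures three-way then two-way test that will actually be run. The change should be made, but it does not call the design into question.

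**What to change.** In Quantitative Analysis, delete the opening condition on significant heterogeneity from both Aim 2 estimation sentences (the one for IBD activity and the one for age and the other moderators). State instead that the interaction estimate, and the TEAM-TECH difference in each level of baseline IBD activity, age and the other pre-specified moderators, will be reported with 95% CIs whatever the p-value. Use the multiplicity-adjusted interaction test only for the confirmatory statement, give the number of tests the adjustment covers, and label the remaining estimates as not confirmatory.

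This brings Aim 2 into line with Aim 1 and with the expectation in the power section. It needs no new data, patients or models: the cost is a wording change, a few more table rows and the label.
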